Lung Imaging of Apoptosis in Chronic Obstructive Pulmonary Disease (COPD)

NCT02978144

IRB approval date: 01/14/2025

BACKGROUND

Study Purpose and Rationale:

Current imaging modalities in lung disease primarily focus on the evaluation of end organ damage and destruction (1). While molecular imaging approaches have been developed in oncology (2-5) and in the assessment of cardiovascular disease (6, 7), the utility of such an approach in lung disease is not yet established. The development of methods to image cellular processes and targets related to disease pathogenesis will allow an evaluation over the time course of disease and provides information as a potential biomarker of disease activity and response to therapy. Chronic obstructive pulmonary disease (COPD) is a major cause of disability and death worldwide and is a progressive lung condition in which tobacco smoke and other stimuli trigger inflammation, production of destructive enzymes and programmed cellular death within the lung (8). Although inflammation can be seen in smokers without COPD, both apoptosis and MMP production are not seen at an increased rate in smokers without COPD (9-12), with the rate of apoptosis correlating with emphysema severity (12). Collaborative studies have successfully developed an imaging approach specifically targeting apoptosis in a pre-clinical model of emphysema (13). These data provide the first evidence of our ability to visualize in vivo with molecular imaging an ongoing cellular process consistent with lung destruction in an animal model of smoke exposure. Molecular imaging offers the advantage of relatively small molecular size probes that can clear from the blood pool and cross capillaries to access receptors or protein antigenic binding sites within tissue, allowing non-invasive functional measurements of disease. This probe (AxV-128/Tc) has already undergone Phase 1 clinical testing for tracer kinetics and radiodosimetry in Canada (12 healthy volunteers, 6 men and 6 women) and the safety profile has been established (see attachment from Advanced Accelerators). We propose to advance into patients this imaging approach with the goal of detecting alterations in pulmonary apoptosis in various stages of COPD. A correlation of known biomarkers with apoptosis imaging will also be assessed. If successful, these imaging techniques will greatly advance the field of pulmonology with clinical imaging modalities to non-invasively assess response to therapies and to potentially guide in prognostication.

Study Design:

This will be a prospective study examining the use of ^{99m}Tc -Annexin V-128 (AxV-128/Tc) SPECT/CT technology in the imaging and functional assessment of the lung of patients with COPD, healthy volunteer smokers without COPD and healthy volunteer subjects without smoking history.

STUDY PROTOCOL

We will study patients with and without lung disease (COPD) and compare AxV-128/Tc SPECT-CT scans. To test the hypothesis that AxV-128/Tc SPECT-CT scanning can detect apoptosis in patients with COPD, we will perform a case control study in patients with varying severity of COPD. There will be four groups of subjects: -Patients with moderate COPD: GOLD Stage II, $\text{FEV}_1/\text{FVC} < 0.7$ and $\text{FEV}_1 < 50\%$ predicted -Patients with severe COPD: GOLD Stage III-IV, $\text{FEV}_1/\text{FVC} < 0.7$ and $\text{FEV}_1 < 50\%$ predicted -Healthy controls who are currently smoking (> 10 pack years) with normal spirometry ($\text{FEV}_1 > 80\%$ and $\text{FEV}_1/\text{FVC} > 70\%$) - Healthy controls who never smoked (less than 100 lifetime cigarettes) with normal spirometry ($\text{FEV}_1 > 80\%$ and $\text{FEV}_1/\text{FVC} > 70\%$) The subjects will undergo spirometry (lung function tests) and blood and urine samples will be drawn prior to undergoing SPECT Scan. The spirometry will ascertain the severity of COPD and blood and urine samples will allow us to measure markers of lung injury as well as cotinine to confirm the smoking status of the subject. Blood samples will be also stored for analysis of biomarkers and possible future DNA and RNA analysis.

Study population: We will study 16 patients with COPD (8 patients with GOLD Stage 2 disease, 8 patients with GOLD Stage 3-4 disease) and 8 healthy volunteer smokers without COPD, and 8 healthy volunteer subjects without smoking history or lung disease to compare AxV-128/Tc SPECT-CT scans in smokers, patients with COPD, and normal control patients.

Recruitment: The patient population will be drawn from the Center for LAM and Rare Lung Diseases, Jo-Ann F. LeBuhn Center for Chest Disease and the Price Family Center for Comprehensive Chest Care and will be stratified by severity of disease. Recruitment of healthy volunteers will be performed with advertisements in Columbia University's "recruitme" website, and flyers throughout the medical center. In order to be eligible, patients with COPD must have a

forced expiratory volume in one second (FEV1) less than 80% of predicted for age and height, and bronchodilatory reversibility of less than 15% or 200 ml with airflow obstruction evidenced by an FEV1/Forced Vital Capacity (FVC) ratio of 70% and FEV1 > 80% of predicted for age and height.

Study Procedures: After obtaining informed consent, the subjects will undergo:

Pulmonary Function Testing: pre- and post-bronchodilator spirometry, lung volume and DLCO measurements.

Urine sample: urinalysis and smoking status will be confirmed by urine cotinine level.

Pregnancy Test: If participant is a woman of child-bearing potential, a urine pregnancy test may be performed to ensure study eligibility. Pregnant women may not participate in this research study as risk of technetium to an embryo or unborn fetus may exist. Women of childbearing potential include all women except those whose menstrual periods have not occurred for more than one year after menopause (change of life) or those who have had sterilization surgery (tubes tied) or hysterectomy (removal of uterus or womb). For women whose menstrual period started less than 4 weeks prior to the study date, a urine dip stick pregnancy test will be performed prior to study drug administration.

Blood sample: Serum biomarkers including leukocyte count, fibrinogen and CRP will be obtained for correlation of these serum biomarkers for COPD exacerbation risk with lung apoptosis-targeted imaging. In addition, apoptotic endothelial microparticles (CD42bCD62E+/CD42bCD31+) will be assessed in order to obtain a direct comparison between imaging signal (%ID) and alternate markers of apoptosis that can be obtained non-invasively.

Repeat PFTs after initial imaging in order to determine the ability of AxV-128/Tc imaging to predict later lung function decline.

SPECT/CT imaging: Vials of AxV-128 provided by AAA will be shipped to Nuclear Diagnostics, a satellite pharmacy that serves Columbia University Medical Center Nuclear Medicine. Nuclear Diagnostics will label AxV-128 with 99mTc and deliver pre-calibrated doses by time of injection to the CUMC Nuclear Medicine Department. Each dose will be injected intravenously by a Medical Doctor (i.e., PI, co-investigators) and if unavailable a certified Nuclear Medicine Technologist (NMT) or Registered Nurse (RN). The injected dose is between 8-10mCi and never more than 10mCi as stated in the IND. Radiation is measured before and residual after injection.

Scans will be performed on Siemen's Symbia T hybrid SPECT/CT (16 slice) scanner in the Nuclear Medicine department. A chest CT scan will be performed with breath hold at the clinical dose using a standard diagnostic CT imaging acquisition protocol. Immediately following the CT acquisition, a SPECT will be performed with a FOV set for the chest from lower neck to upper abdomen. Standard CT acquisition protocols will be used.

Vitals: Vitals will be obtained at two time points: before injection of tracer/blood draw and after the SPECT/CT imaging has been performed. Vital signs indicate the status of a person's life-sustaining functions including: Blood pressure, Heart rate and oxygen saturation rate. These measures will be recorded for safety purposes only.

Medical History: Medical history including diagnoses and current medications taken will be collected during the study visit. Participants are encouraged, but not required to provide outside medical documentation confirming COPD or Alpha-1 diagnosis or any recent Pulmonary Function Testing, blood work and imaging done clinically. Study investigators will review any outside medical documentation and determine if any study procedures may be substituted for outside clinical records as to not burden participants repeating exams already done clinically.

Follow up calls: One of the study team members will conduct follow up phone calls at 24-72hours, 1 month and 6 months post imaging. These calls will be done for safety purposes only and will only take 1-2 minutes. Information collected includes any reporting of side effects and any medical diagnosis or medication changes.

Reproducibility (Short and Long Term): In order to document short term reproducibility of the imaging method and give an assessment of a meaningful change of signal in a patient, up to 10 of the subjects with COPD (from either the moderate or severe COPD groups) will undergo repeat AxV-128/Tc SPECT/CT scans within one week of the original scan. Patients will not undergo repeat imaging if there has been a significant change in their clinical status including a COPD exacerbation pulmonary infection, or CHF exacerbation. Repeat imaging will only be performed on patients with COPD as it is anticipated based upon literature documenting that never smokers have negligible levels of apoptosis within the lung. The Phase I data of AxV-128/Tc with normal subjects also demonstrated less than 5% ID lung uptake. Smokers without disease will be excluded from this reproducibility study as smoking may be variable from day to day and may alter signal results.

In addition, long term changes in this imaging method will be assessed on subjects with COPD with an additional AxV-128/Tc SPECT-CT scan and same procedures listed above. The follow up visit may be done without an additional AxV-128/Tc SPECT-CT scan and same procedures listed above. Please note that only a SUBSET of subjects will undergo 1 year or 1 week repeat scan. One year follow up visits are approximate 1 year +/- 8 months. This is to compensate for coordinating contacting participant and scheduling visits around their most convenient time.

Imaging and data analysis: Mean \pm SD for values for uptake of AxV-128/Tc for individual lobes and for lungs will be determined for each COPD group and compared using unpaired t-test for values with Gaussian distribution and Mann-Whitney (Wilcoxon rank) test for continuous variables without normal distribution. Gaussian distribution will be determined using the Kolmogorov-Smirnov test. We have included moderate, severe and very severe COPD patients assuming that the signal will increase with the severity of COPD. We could therefore establish an exposure-response relationship between severity of COPD (on a non-linear scale) and signal. This assumption is based upon our work establishing a correlation between COPD severity and apoptotic index in the lung (12). Mean \pm SD for values for volumes and Hounsfield units will also be compared among the same groups. We will also assess tracer uptake normalized for lung volumes. In the emphysema patients we are measuring a signal coming from living (and dying) tissue that is interspersed in air. In the more severe cases of COPD, the lung tissue takes up less volume within the lungs and the air forms greater percent of each lobe. We will attempt to account for these changes by normalization for Hounsfield units. In addition values for %ID tracer uptake will be correlated with values for PA:A ratio. For the serial reproducibility studies, the values for whole lungs and lobes from the two studies will be analyzed for agreement using Bland-Altman analysis.

Incidental finding of clinical significance: Potential incidental findings of clinical significance that may be discovered during imaging procedure may include tumors, hematomas, infectious complications such as abscesses and vascular abnormalities among others.. The following procedures pertain to the finding of incidental findings (IF) that may occur during the imaging of the subjects. The images will be read by a radiologist credentialed by the Department of Radiology as soon as possible but no later than two weeks following receipt of the image. Imaging will only take place at Columbia University Medical Center. If the credentialed

radiologist will find an IF with clinical significance this will be recorded in the research record and the subject will be notified by the PI who is a critical care physician either in person or by phone followed by a letter or email.

If an IF has been reported we will notify the IRB during the next review about the number of Required Review Images, a list of the subject study numbers, the type of scan, the date of the scan, a description of the IF of Clinical Significance, the date of communication with the subject and the outcome, if known.

Eligibility Criteria

Inclusion Criteria:

1. Males and females age 45-80 years
2. Able and willing to comply with the study procedures
3. Gold class II COPD or greater
4. Healthy Smoker
5. Healthy non-smoker
6. Lie flat for 30 minutes

Exclusion Criteria:

1. Current Malignancy
2. Bronchiectasis
3. Recent COPD exacerbation (less than 1 month)
4. Recent pulmonary infection (less than 1 month)
5. Asthma or other significant lung disease
6. Pregnancy or lactation
7. Claustrophobia or inability to lie still in a supine position

RESEARCH AIMS & ABSTRACTS

Research Question(s)/Hypothesis(es):

We hypothesize that there will be an increased AxV-128/Tc signal in the lungs of patients with COPD as compared to control patients. This signal is hypothesized to be higher in patients with more severe COPD.

Scientific Abstract:

Chronic obstructive pulmonary disease (COPD) is the third leading cause of death and is characterized by clinical symptoms and spirometry. Additional measures for diagnosis can be taken using imaging modalities such as CT. However, the evaluation of lung destruction in COPD is limited by the inability to visualize the activation of pathological processes since imaging modalities are only able to evaluate end-organ damage. In this proposal, we aim to assess a molecular imaging probe targeting apoptosis, a cellular process known to be pathogenic in COPD. Apoptosis, a process of programmed cellular death, correlates with COPD severity and is not seen in the normal adult lung. In the past several years we have demonstrated the successful ability of AxV-128/Tc to detect apoptosis *in vivo* in a rabbit smoke exposure emphysema model. Additionally, Phase 1 studies have demonstrated safety of this agent in healthy patients. Therefore, we will bring AxV-128/Tc forward as a probe to image the apoptotic disease process of the lung in patients with COPD. We will determine if the imaging signal correlates with serum biomarkers of apoptosis and inflammation. It is our hypothesis that AxV-128/99mTc imaging will show increased uptake in the lungs of patients with COPD, and that this signal intensity will correlate with accepted markers of apoptosis and inflammation. If successful, such an approach will be a powerful tool to potentially predict disease progression after diagnosis, identify patients at risk for disease exacerbation related lung function decline, and monitor response to disease targeted therapy. The total effective dose from the combined SPECT and CT scans is 6.71 mSv. This effective dose is below what a patient receives during a standard 2 dose rest and stress cardiac nuclear imaging study and well within the range of current clinical nuclear imaging tests. The exact long term risk for development of cancer from diagnostic radiological procedures is currently under debate but all imaging procedures in this study are aimed to keep total radiation burden ALARA (As Low As Reasonably Achievable).

STATISTICAL PROCEDURES

Serum biomarkers of inflammation and levels of apoptotic endothelial microparticles will be correlated with % injected dose of radiotracer on SPECT-CT imaging results. Up to ten patients with COPD will undergo a second SPECT-CT scan within 1 week of the first baseline/visit#1 scan in order to determine the short-term reproducibility of the signal and to determine what would be a meaningful change in signal. Patients must be clinically unchanged in the intervening week. A subset of COPD diagnosed subjects will undergo a repeat scan after 1 year of the baseline/visit#1 scan; this will include repeat SPECT-CT, pulmonary function testing, blood and urine testing. The purpose of the repeat imaging to determine (1) the ability of the initial scan to determine later lung function decline and (2) if change in signal over a 1 year time point is associated with meaningful clinical change. In addition, we will compare SPECT-CT signal (percent injected dose, %ID) as a primary endpoint, apoptotic endothelial microparticles and serum biomarkers of inflammation in patients with COPD, smoking history without COPD, and healthy non-smoking control participants. There is no human data of AxV-128/Tc SPECT-CT imaging in lung disease that would allow us to determine an appropriate sample size for this study. We will therefore base this on our rabbit studies (13) which found a %ID of approximately $0.645 +/ - 0.427\%$ in animals without and $2.0 +/ - 0.589\%$ in animals with smoke exposure with a common standard deviation of $(0.63+0.589) / 2 = 0.508\%$. We will need 5 patients per group to achieve a power of 80% and a confidence level of 99%. We will recruit 8 subjects who never smoked and are without lung disease, 8 patients who were smokers without lung disease, and 16 patients with COPD (8 with GOLD Stage 2 disease and 8 with Gold Stage 3-4 disease). Eight patients per group will give us sufficient power even when compensating for increases in variability in human subjects.

REFERENCES

1. Washko GR. Diagnostic imaging in COPD. *Semin Respir Crit Care Med.* 2010;31(3):276-85.
3. Everitt S, Hicks RJ, Ball D, Kron T, Schneider-Kolsky M, Walter T, Binns D, Mac Manus M. Imaging cellular proliferation during chemo-radiotherapy: a pilot study of serial 18F-FLT positron emission

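### The moderate and severe COPD groups carry the same printed FEV1 limit, so only their GOLD labels separate them, and eligible patients from 50% to under 80% predicted meet neither group's limits

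*Combined protocol and SAP*

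**What the plan says.** The list of four groups under STUDY PROTOCOL in the combined protocol and SAP opens with this definition: "Patients with moderate COPD: GOLD Stage II, $\text{FEV}_1/\text{FVC} < 0.7$ and $\text{FEV}_1 < 50\%$ predicted". The entry that follows it covers the other COPD group and changes the severity word and the stage, but neither of the two numeric limits: "Patients with severe COPD: GOLD Stage III-IV, $\text{FEV}_1/\text{FVC} < 0.7$ and $\text{FEV}_1 < 50\%$ predicted".

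The same section says "The spirometry will ascertain the severity of COPD". The Study population paragraph sets quotas by stage: "8 patients with GOLD Stage 2 disease, 8 patients with GOLD Stage 3-4 disease". STATISTICAL PROCEDURES repeats these quotas. The Recruitment paragraph says the patient population "will be stratified by severity of disease" and requires COPD patients to have a "forced expiratory volume in one second (FEV1) less than 80% of predicted for age and height". The Inclusion Criteria ask only for GOLD class II or above and give no FEV1 figure.

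Two places depend on the split. Imaging and data analysis states "We have included moderate, severe and very severe COPD patients assuming that the signal will increase with the severity of COPD" and from this expects an exposure-response relationship. The Research Question(s)/Hypothesis(es) paragraph predicts a stronger signal in more severe disease.

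**The concern.** Two groups meant to differ in severity share one ratio limit and one FEV1 limit, although spirometry is the stated means of judging severity. To place a patient, staff must either bring in a GOLD definition that the documents do not print, or apply a number that does not discriminate between the groups. The number also fits poorly with eligibility. If both COPD groups require FEV1 below 50%, the 80% limit in the Recruitment paragraph does no work.

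What is at stake is the moderate-versus-severe comparison, and with it the severity hypothesis and the exposure-response aim. With 8 subjects per group, one misplaced patient is 1/8 = 12.5% of a group. A secondary matter is the make-up of the COPD sample that is compared with controls on the primary endpoint, %ID.

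**Working it through.** **Inputs.** Moderate group: GOLD II, ratio below 0.7, FEV1 below 50% (STUDY PROTOCOL). Severe group: GOLD III-IV, ratio below 0.7, FEV1 below 50% (same list). COPD eligibility: FEV1 below 80% (Recruitment). Planned sizes: 8 moderate, 8 severe, 8 smokers without COPD, 8 never-smokers (Study population; STATISTICAL PROCEDURES).

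**Step 1: apply the printed FEV1 limits.** Take whole-number FEV1 values from 20% to 79% predicted, with the ratio limit met.

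| FEV1, % predicted | Eligible (below 80%) | Moderate limit | Severe limit |
|---|---|---|---|
| 20 to 49 | yes | met | met |
| 50 to 79 | yes | not met | not met |

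No value meets one limit without the other. The uncovered band is 80 - 50 = 30 percentage points wide. This is a gap in coverage and not a logical contradiction, since below 50% lies inside below 80%. The documents give no FEV1 distribution, so the share of eligible patients in the band is unknown.

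**Step 2: look for a repair elsewhere.** The Inclusion Criteria, Imaging and data analysis, and STATISTICAL PROCEDURES use stage names or severity words only. None prints an FEV1 range for GOLD II or a figure dividing II from III-IV.

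**Step 3: how many subjects the line defines.** 8/16 = 50% of COPD subjects; 8/32 = 25% of all subjects.

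**Step 4: consequences under each way of using the definition.**

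- *Label only.* Groups are formed by GOLD stage and the printed number is ignored. Subjects affected: 0 of 8.
- *Label and printed limit together.* Every COPD subject must be below 50%: 8 + 8 = 16 of 16. The severe group's limit alone would require this of 8 of 16. Milder eligible patients are left out. Because the GOLD ranges are not printed, the documents cannot show whether any patient satisfies both the stage II label and the limit.
- *Printed limit alone.* The two groups are the same set, so the rule gives no way to fill 8 + 8. This reading cannot be operated.

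**Step 5: sample size.** The stated 5 per group comes from rabbits with and without smoke exposure: difference 2.0 - 0.645 = 1.355, SD 0.508 as stated, alpha 0.01, power 80%. The two-sided normal approximation gives 4 per group. The t distribution gives 6 two-sided and 5 one-sided. The stated figure is therefore reproduced approximately, and it does not use the moderate/severe split. No power is computed for that split, because the documents hold no human moderate-versus-severe effect size.

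**The case against.** The strongest reply is that the written rule has three parts and one of them does separate the groups. GOLD II and GOLD III-IV are different labels, the quotas are set by stage in two sections, and the Inclusion Criteria are also by stage. One figure on one line is out of step, which looks like a copying slip. Identical limits alone could not fill the quotas, so staff must have used the label. This stands, and it rules out a reading that a reader might infer: that the protocol has no means of telling the groups apart. The documents support only the narrower statement about the numeric limits.

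A second reply is that the text may have been misread from the PDF. The end of the COPD eligibility sentence in the Recruitment paragraph is visibly garbled, and nothing here relies on that end. The two group definitions are complete and well formed, so damage there is possible but not shown. The source file has to settle it.

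A third reply is that the primary comparison needs no split. STATISTICAL PROCEDURES treats COPD as one category against smokers without COPD and never-smokers. This also stands. A reader might infer that the COPD-versus-control difference is biased upward. That would follow only if the printed limit was enforced and the plan's assumption that signal rises with severity is true. The documents show no sign of the first and give no size for the result. Nor can one count how many group contrasts are spoiled, because the plan names two-sample tests without listing the contrasts.

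What the replies do not remove is that the number remains in force for the moderate group beside the label, and no section says which prevails.

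**Conclusion.** The point holds in narrow form. As printed, the numeric limits of the moderate and severe groups are identical, and a 30-point band of eligible FEV1 meets neither. Only the GOLD labels separate the groups, and their ranges are not given.

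The definition of 8 of 16 COPD subjects is affected, and so is the basis of the moderate-versus-severe comparison. The practical effect lies between none (label followed) and a COPD sample in which all 16 subjects are below 50% (printed limit also enforced). The documents do not show where in that range the trial fell. Any effect on COPD versus controls is conditional and of unknown size, and the sample size calculation is untouched.

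This rests on two assumptions: that the group definitions were read correctly from the source, and that the legible part of the eligibility sentence, FEV1 below 80%, is as intended. The correction is cheap and a stated hypothesis depends on it, so it should be made before the COPD groups are compared.

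**What to change.** 1. Check the source file for the group definitions under STUDY PROTOCOL and for the COPD eligibility sentence under Recruitment.
2. If the text is as printed, reconcile the moderate group's FEV1 limit with its GOLD label, with the below-80% eligibility limit and with the GOLD class II or greater criterion. The two groups should be mutually exclusive and together cover every eligible COPD patient. The choice of limit is for the sponsor.
3. State which spirometry value assigns the group. Study Procedures collects both pre- and post-bronchodilator values, and the Medical History paragraph lets outside records replace study tests, so both choices need to be named.
4. Confirm each enrolled COPD subject's group from that recorded value, without reference to %ID results.
5. Report the actual group sizes and the FEV1 range in each group.

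The cost is a wording amendment and a check of up to 16 records, with no new procedures or subjects. The drawback is that the 8/8 split may turn out not to hold. The moderate-versus-severe result would then have to be reported with the sizes actually obtained.

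### A pregnancy test before the tracer is required for only part of the group the protocol defines as of childbearing potential; for the rest it is optional

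*Combined protocol and SAP*

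**What the plan says.** The Pregnancy Test paragraph under Study Procedures (combined protocol and SAP) sets two levels of obligation.

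- For the whole group the test is permitted: "If participant is a woman of child-bearing potential, a urine pregnancy test may be performed to ensure study eligibility".
- For one subgroup it is mandatory, and must come before the tracer is given: "For women whose menstrual period started less than 4 weeks prior to the study date, a urine dip stick pregnancy test will be performed".

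The same paragraph defines the group broadly: "Women of childbearing potential include all women except those whose menstrual periods have not occurred for more than one year after menopause". Its only other exceptions are sterilization surgery and hysterectomy. It also gives the reason for the exclusion: "Pregnant women may not participate in this research study as risk of technetium to an embryo or unborn fetus may exist".

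Under Eligibility Criteria, exclusion 6 reads "Pregnancy or lactation", with no test or timing attached. Inclusion criterion 1 is "Males and females age 45-80 years". In the imaging section, the injected dose is 8 to 10 mCi, and "A chest CT scan will be performed with breath hold at the clinical dose".

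**The concern.** Within one paragraph, *may* governs the general group and *will* governs a narrower one. Staff who follow the text would reasonably take the two words to mean different things. The dividing line is also odd. Taken at face value, a woman whose period began recently must be tested, while a woman whose period may be overdue need not be, although she is the one in whom an unrecognized pregnancy is the greater worry.

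What is at stake is exposure of an embryo or fetus to a radiotracer and a chest CT in a study with no therapeutic aim for the participant; half of the planned subjects (16 of 32) are healthy volunteers. The protocol itself cites possible technetium risk as its reason for the exclusion. The primary endpoint, the group comparisons and the sample size are not touched.

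**Working it through.** No arithmetic applies. The check is whether the required test, together with anything else in the document, covers every woman whom the protocol defines as of childbearing potential.

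**Step 1: split the group by the protocol's own cut-off.** Take women who meet none of the three exceptions (more than a year without periods after menopause, sterilized, hysterectomy).

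- Group A: last period began less than 4 weeks before the study date.
- Group B: last period began 4 or more weeks before. This includes late, skipped and irregular periods, and women who have stopped menstruating but not yet for long enough to be exempt.

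**Step 2: apply the testing sentences under each plausible reading of the cut-off.**

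| Reading of the 4-week sentence | Group A | Group B |
|---|---|---|
| Literal | required | optional |
| Meant to pick out women still menstruating | required | optional |
| *Less than* is a slip for *more than* | optional | required beyond 4 weeks |

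No row has a required test in both columns. The missed-period scenario arises in the first two rows only. In the third, the woman with a possibly missed period is tested and the remaining gap is women with a recent period, which is a lesser concern.

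**Step 3: look for another provision that closes the gap.**

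- Exclusion 6 bars pregnancy but prescribes no test.
- The Urine sample item lists urinalysis and cotinine, not a pregnancy test.
- The Medical History item says "Medical history including diagnoses and current medications taken will be collected during the study visit". The word *including* leaves room for more, but the date of the last period, on which the mandatory sentence depends, is not named.
- The section on short- and long-term reproducibility applies the same procedures to the 1-year repeat scan, so it carries the Pregnancy Test paragraph forward, gap included. It does not say this for the 1-week repeat.

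Nothing visible makes the test mandatory for the uncovered part.

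**Step 4: size.** The Study Protocol section plans 8 + 8 + 8 + 8 = 32 subjects. The documents give no split by sex or menopausal status, so the number of women affected cannot be calculated. The Scientific Abstract gives a total effective dose of 6.71 mSv for the combined SPECT and CT scans. That is the participant's dose; no embryo dose is given, so harm cannot be quantified.

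**The case against.** The strongest reply is that the safeguard is largely present. Pregnancy is barred twice, and the urine test is named, for the purpose of confirming eligibility, for every woman of childbearing potential. The 4-week sentence exempts nobody. An investigator faced with a possibly missed period has both a duty to exclude pregnancy and a stated means of doing so. This stands, and it limits the point: a reader might infer that the protocol has no way of ruling out pregnancy, and the text does not support that. Only the obligation is missing.

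A second reply is that the lay glosses in the paragraph suggest consent-style wording in which *may* was loosely meant as *will*. That is possible. If so, the 4-week sentence adds nothing but the timing, and the amendment merely states what was intended. The consent pages and the IND are not available here, so what they require cannot be checked.

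A reader might also infer that the cut-off is plainly reversed. The documents do not say so; it could equally be a clumsy marker for women still menstruating. The point does not depend on settling this, but the missed-period scenario does: it holds only if *less than* is taken as written.

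Finally, the reach is very small: 32 subjects aged 45 to 80. That is conceded. On the other hand, the protocol saw fit to define childbearing potential and to require a test for some women in this age range, and irregular periods around the menopause would place women in the optional group on the literal reading.

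**Conclusion.** The point holds as a gap in obligation. The visible text requires a test before the tracer for only part of the group it defines as of childbearing potential, whichever way the 4-week cut-off is read. On the literal reading, the uncovered part includes women with a possibly missed period. The number affected is probably very small and may be zero. That is a judgment from the age range and the planned enrollment, not a calculation.

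The conclusion rests on the visible text alone. It does not imply that any pregnant woman has been or would be scanned, nor that staff would fail to test. It changes no endpoint, comparison or sample-size figure. The change is worth making because the possible consequence is serious and avoidable and the remedy costs almost nothing.

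**What to change.** Keep the definition of childbearing potential and exclusion 6 as they are. In the first sentence of the Pregnancy Test paragraph, replace the permissive verb so that, for every woman of childbearing potential as defined there, a urine pregnancy test *will be performed, and must be negative, before each AxV-128/Tc administration*. Delete the 4-week sentence, which then has no function.

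Wording it per administration matters because subsets of COPD patients are injected again: up to 10 within one week, and some at about 1 year (plus or minus 8 months). A negative baseline test says little about the later scan.

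The cost is a short amendment and a few extra dipsticks. Urine is already collected before the baseline scan (Study Protocol) and at the 1-year repeat (Statistical Procedures). No urine collection is listed for the 1-week repeat, so an extra sample may be needed there from any woman of childbearing potential in that COPD subset.
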